Appendix

Version Date: 05/25/2023 Page 2 of 13

Abbreviations

This page is optional. The list below includes some common abbreviations. However, this list should be customized for each protocol (i.e., abbreviations not used should be removed and new abbreviations used should be added to this list).

۸۲	Advance French				
AE	Adverse Event				
CFR	Code of Federal Regulations				
CLIA	Clinical Laboratory Improvement Amendments				
CMP	Clinical Monitoring Plan				
COC	Certificate of Confidentiality				
CRF	Case Report Form				
DCC	Data Coordinating Center				
DHHS	Department of Health and Human Services				
DSMB	Data Safety Monitoring Board				
DRE	Disease-Related Event				
eCRF	Electronic Case Report Forms				
FDA	Food and Drug Administration				
FDAAA	Food and Drug Administration Amendments Act of 2007				
GCP	Good Clinical Practice				
GLP	Good Laboratory Practices				
GMP	Good Manufacturing Practices				
GWAS	Genome-Wide Association Studies				
HIPAA	Health Insurance Portability and Accountability Act				
IB	Investigator's Brochure				
ICH	International Conference on Harmonisation				
ICMJE	International Committee of Medical Journal Editors				
IDE	Investigational Device Exemption				
IND	Investigational New Drug Application				
IRB	Institutional Review Board				
ISM	Independent Safety Monitor				
ISO	International Organization for Standardization				
MedDRA	Medical Dictionary for Regulatory Activities				
MOP	Manual of Procedures				
NCT	National Clinical Trial				
NIH	National Institutes of Health				
OHRP	Office for Human Research Protections				
PI	Principal Investigator				
QA	Quality Assurance				
QC	Quality Control				
SAE	Serious Adverse Event				
SAP	Statistical Analysis Plan				
SMC	Safety Monitoring Committee				
SOA	Schedule of Activities				
SOP	Standard Operating Procedure				
UP	Unanticipated Problem				
US	United States				

Version Date: 05/25/2023 Page 3 of 13

1.0 Background & Rationale

First introduced in the 1990's, enhanced recovery after surgery (ERAS) is a multimodal perioperative approach to surgical recovery, shown to lead to early recovery and improved outcomes (1). One of the primary objectives of ERAS programs is appropriate pain control with reduction of postoperative opiate consumption. The mainstay by which most ERAS programs accomplish this goal is an interplay between NSAID's, acetaminophen and local anesthesia. For patients undergoing pelvic organ prolapse repair -following implementation of ERAS programs-it has been shown that patient post discharge recovery is greatly improved and that postoperative opiate consumption is significantly decreased (2,3). In one study of patients undergoing open gynecologic procedures, they were found to have a reduction of mean opioid consumption of 72% with 16% of the patients opioid free prior to discharge (4). Additionally, it has been well documented that patients who undergo gynecologic or pelvic reconstructive surgery are overprescribed opiates at the time of discharge (5). It is recommended that opiate naïve patients be discharged with no more than 15 doses of a given narcotic and that these patients be individualized, as many will require less (5,6).

One of the more controversial and under-investigated aspects of postoperative pain control in the field of Female Pelvic Medicine and Reconstructive Surgery (FPMRS) is the use intraperitoneal local anesthesia.

The two type of peritoneum in the human body are the parietal peritoneum (PP) and visceral peritoneum (VP). The PP is innervated by the somatic nervous system, leading to the perception of localized, sharp pain (7). The VP has sub-mesothelial tissue innervated by the autonomic nervous system, responding to traction, distension and pressure, leading poorly localized, dull pain (7). We also know that the peritoneum is a highly permeable membrane given its long-term use in peritoneal dialysis (8). Due to blockade of free afferent peritoneal nerve endings, it is plausible that intraperitoneal local anesthesia has a role in management of postoperative pain.

It has been documented that infiltration of local anesthetics has been shown to effectively control postoperative pain for patients undergoing laparoscopic, open and vaginal gynecologic procedures (9, 10, 11), but data is still limited as to the role of intraperitoneal local anesthetic lavage during pelvic reconstructive surgery. Two studies looking at the use of intraperitoneal lidocaine lavage at the time of total abdominal hysterectomy found that this offered improvement of pain control for 12 to 24 hours following the procedure with no associated reduction in opiate consumption (12, 13). In contrast, an RCT performed looking at the effectiveness of intraperitoneal Bupivacaine following laparoscopic pelvic surgery, appreciated significant improvement in pain (as demonstrated on a visual analog scale) and a decrease in analgesic requirement (14). There is also literature demonstrating improvement in patients perceived intraoperative discomfort at the time of postpartum tubal ligation, who receive intraperitoneal lidocaine (15).

While there are some studies in gynecologic literature, most studies are present in anesthesia, general surgery, colorectal surgery and bariatric surgery literature (9, 16-20). In a systematic review of 41 RCT's, 13 trials were identified comparing intraperitoneal Bupivacaine vs Lidocaine vs saline for patients undergoing laparoscopic cholecystectomy (9). In that review, seven of the 13 trials reported improved pain relief compared to placebo, with effects lasting between 2-24 hours (9). A recent RCT from bariatric surgery literature evaluated the effects of intraperitoneal

Version Date: 05/25/2023 Page 4 of 13

Bupivacaine vs placebo in patients undergoing bariatric surgical procedures. In this study, 106 patients were assigned to receive intraperitoneal lavage with 50 mL of 0.2% Bupivacaine or the same volume of normal saline during the procedure. Using a VAS, patients postoperative pain was rated at 1, 4, 8 and 24 hours after surgery. This study found statistically significant decreased pain scores and opiate consumption among the Bupivacaine group for the first 24 hours after surgery (19). Studies have also been performed evaluating the use of intraperitoneal Bupivacaine vs Tramadol for management of postoperative pain during same day laparoscopic surgery. In a randomized trial of 90 patients assigned to intraperitoneal Bupivacaine (20 mL at 0.25%), IV tramadol hydrochloride (2 mg/kg), intraperitoneal saline (20 mL) or IV saline (2 mL) appreciated better analgesic outcomes among the Bupivacaine group (21).

Of the local anesthetic options available, Bupivacaine is known to have a longer duration of action compared to its counterparts (22). The maximum dose of Bupivacaine that should be administered is 2.0 mg/kg without epinephrine and 2.5 mg/kg with epinephrine (22). Therefore, the maximum allowable dose of Bupivacaine without epinephrine 0.25% should not exceed 56 mL in a 70 kg patient. While toxicity caused by local anesthesia can have CNS (nausea, vomiting, chills, pupil constriction, tinnitus, nervousness, dizziness, blurred vision, or tremors, followed by drowsiness, convulsions, unconsciousness, and possibly respiratory arrest as noted in the package insert) and CVS (depression of the myocardium, decreased cardiac output, heartblock, hypotension, bradycardia, ventricular arrhythmias, including ventricular tachycardia and ventricular fibrillation, and cardiac arrest as noted in the package insert when high doses or unintentional intravascular injection is administered) manifestations, these formulations have relatively wide safety margins and toxicity only occurs when these thresholds are exceeded (22, 23). One systemic review set out to evaluate the safety profile and systemic levels of local anesthesia following intraperitoneal administration (23). In this review, 415 patients were included, 11 (2.7%) were found to have systemic levels close to or above threshold and no cases of clinical toxicity were observed (23).

The purpose of this study is to evaluate the effects of 30 mL intraperitoneal Bupivacaine without epinephrine 0.25% on postoperative pain control in patients undergoing pelvic organ prolapse repair. We hypothesize that use of intraperitoneal Bupivacaine will decrease postoperative pain scores and opiate consumption in the postoperative period, following pelvic organ prolapse repair.

2.0 Objective(s)

- 2.1 Primary Objective
- 2.2 Secondary Objective

2.1: To determine whether intraperitoneal Bupivacaine will decrease pain scores at approximately 4 hours, as determined by a numeric rating scale (NRS) in patients undergoing pelvic organ prolapse repair.

Version Date: 05/25/2023 Page 5 of 13

2.2: Pain scores as determined by NRS at approximately 8, 12 and 24 hours, total opiate consumption postoperatively while inpatient as determined by morphine milligram equivalents (MME), time to first narcotic dose during inpatient stay, and hospital length of stay.

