3.0 Outcome Measures/Endpoints

- 3.1 Primary Outcome Measures
- 3.2 Secondary Outcome Measures
- 3.1: Patient pain will be measured by means of a NRS at 4 hours after surgical pelvic organ prolapse repair.
- 3.2: Patient pain will be measured by means of a NRS at 8, 12 and 24 hours after surgical pelvic organ prolapse repair. Total opiate consumption will be measured in MME, obtained from the electronic medical record. Time to first narcotic dose will be measured in hours and minutes. Hospital length of stay will be measured in days, hours and minutes.

Patients receiving an opioid prescription after short stay surgeries have a 44% increased risk of long term opioid use. The first 4-24 hours postoperatively is the time when these prescriptions are provided. With appropriate control of postoperative pain in the first 4-24 hours, patients may be able to be discharge without opiate prescription.

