7.0 Study Procedures

In the study, patients will be randomized to one of two groups. Arm 1 will be participants who receive intraperitoneal bupivacaine and arm 2 will be participants who receive placebo (saline).

All patients involved in the study will be undergoing pelvic organ prolapse surgery with peritoneal access and will receive either 30 mL of 0.25% Bupivacaine or 30 mL of saline by means of intraperitoneal lavage. This will be performed at which point peritoneal access will no longer be available, and the solution will be left in the abdomen upon completion of the procedure.

Preoperatively, patients will receive a standardized pain control regimen of Ibuprofen and Tylenol in accordance with hospital ERAS protocol. Postoperatively, patients will receive standardized pain control regimen of Ibuprofen and Tylenol in accordance with hospital ERAS protocol. Patients can be given as needed narcotics if pain is poorly controlled on the initial regimen.

All patients will have pain scores measured at approximately 4 hours using a NRS following completion of the procedure. All patient will have pain scores measured at approximately 8, 12 and 24 hours by means of text message NRS (in the event of same day surgery discharge) vs inpatient in person NRS (for planned admission), following completion of the procedure, which will be stored directly into REDCap. Time to first narcotic dose will be obtained through the hospital electronic medical record. Hospital length of stay will be obtained through the hospital electronic medical record.

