12.0 Statistical Considerations

Sample size/Power

This is a double-blind randomized controlled study to compare two techniques of pain management strategies for woman undergoing advance-organ prolapse surgery with the primary outcome being the numeric rate scale (NRS) at 4 hours post-surgery. Secondary outcomes will be the NRS collected at 8, 12, and 24 hours, and an indicator of whether woman required opioids (Y/N) within 4 hours of surgery.

Assuming a SD = 2.14^2 in the NRS at 4 hours, to detect a meaningful change of 1.3 would be an ES = 0.60 (1.3/2.14). To have 80% power to detect an effect size of this magnitude (i.e., a 0.6 SD difference in the NRS between treatment arms) based on a two-sided two-sample independent t-test with type I error set at 0.05 requires a total sample size of N = 90 (45 per group). As we expect no attrition or missing data on the primary outcome, N = 90 will be our planned sample size.

Randomization

Patients will be randomized 1:1 to the two pain strategies using stratified randomization with surgery technique being the strata. Block randomization will be used with blocks of size 4. Randomization lists will be constructed by the study statistician using statistical software.

Statistical Methods

Descriptive statistics of N, mean, standard deviation, median, minimum, and maximum or frequency and percent will be provided for all baseline characteristics overall and by treatment arm. Baseline characteristics which will be reported include surgical procedure (uterosacral ligament suspension vs sacrocolpopexy), age, BMI, menopausal status, surgical time, and intraoperative complications. Intraoperative complication will be a dichotomous variable of whether any complication occurred (Y/N). Baseline characteristics will be compared between the two study arms to verify randomization achieved balanced groups. Any characteristics that significantly differ will be considered in subsequent analyses.

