Assuming baseline characteristics are balanced between the two study arms, we will use a linear mixed model fit to all timepoints (4, 8, 12, and 24 hours) with effects of surgery technique, treatment group, time, and the time x treatment group interaction to estimate the mean difference in treatment groups at each time point. All model assumptions will be checked for adequacy. The mean difference and 95% confidence interval at each time point will be reported. A p-value of 0.017 will be used to indicate statistical significance in the NRS collected at the three other time points (8, 12, and 24) to maintain familywise type I error at .05. For

Version Date: 05/25/2023 Page 10 of 13

the dichotomous outcome of whether patients required opioids in the first 4 hours following surgery, a Fisher's exact test will be used.

Other outcomes can only be assessed among those that required opioids thus will have lower power. Thus, caution will be used in interpretation of results. These include the amount of MME in the first four hours and time to first dose. Descriptive statistics by study group will be estimated. For outcomes which may be normal, then a linear regression model will be fit with effect of surgery technique and treatment, to estimate the mean difference in the outcome by treatment and associated 95% confidence interval. If any outcome is non-normal, then a generalized linear regression model will be used instead with an appropriate distribution and link function to detect the effect of treatment.

- 1. Cohen J. Statistical power analysis for the behavioral sciences. L. Erlbaum Associates; 1988.

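### The opioid-consumption objective (whole inpatient stay) has no specified analysis; Section 12 analyses first-four-hour MME among opioid users only, and the inpatient total stops at discharge with home doses uncollected

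*Combined protocol and SAP*

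**What the plan says.** The combined protocol and SAP describes opioid consumption in three places, in three ways.

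- **Section 2.2 (secondary objective):** "total opiate consumption postoperatively while inpatient as determined by morphine milligram equivalents (MME"). The window is the hospital stay, whatever its length.
- **Section 3.2 (outcome measures):** "Total opiate consumption will be measured in MME, obtained from the electronic medical record". No window is given, and the hospital record is the only source named.
- **Section 12.0 (Statistical Considerations):** the list of secondary outcomes contains "an indicator of whether woman required opioids (Y/N) within 4 hours of surgery" and no MME total. MME appears later, under a paragraph that opens "Other outcomes can only be assessed among those that required opioids thus will have lower power" and goes on "These include the amount of MME in the first four hours and time to first dose".

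Two further statements bear on the inpatient total. Section 7.0 collects later pain scores by "text message NRS (in the event of same day surgery discharge) vs inpatient in person NRS (for planned admission"), so some patients leave within hours and others stay. Section 3.2 makes the length of that stay a secondary outcome in its own right: "Hospital length of stay will be measured in days, hours and minutes". The NRS is the only item that Section 7.0 describes collecting after discharge.

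**The concern.** Lower opiate consumption is half of the hypothesis stated at the end of Section 1.0, so the reader should be able to tell which number will answer it. Three things stand in the way.

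1. **Objective and analysis do not match.** Either the whole-stay total or the four-hour amount could later be presented as opioid consumption, and the choice could be made after the data are seen.
2. **The analysed amount is conditioned on a post-randomisation event.** If bupivacaine spares some patients any opioid, the users left in that arm are no longer comparable with users in the placebo arm. The mean among users could stay level or rise while consumption in the whole arm falls.
3. **The inpatient total has a different observation time for each patient.** It closes at discharge, and the plan itself treats discharge time as something that treatment may change. Doses taken at home are not seen, although Section 3.0 singles out the first 4 to 24 hours as the period that matters for discharge prescribing.

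**Working it through.** **Step 1. The definitions side by side.**

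| Place | Quantity | Window | Patients |
|---|---|---|---|
| Section 2.2 | total MME | inpatient stay | not restricted |
| Section 3.2 | total MME from the medical record | none stated | not restricted |
| Section 12, outcome list | any opioid, Y/N | 4 h | not restricted |
| Section 12, methods | MME | first 4 h | those who required opioids |

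No row of Section 12 matches Section 2.2 in window or in patients. The restriction to users is also unnecessary for an amount, because a patient who took no opioid has an observed value of 0 MME. This step needs no assumption.

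**Step 2. The plan's own figure.** The only sample-size figure concerns the 4-hour NRS. The effect size is 1.3/2.14 = 0.607, used as 0.60. A two-sided t-test at 0.05 with 80% power needs 44.6, so 45 per arm and N = 90; power at 45 per arm is 80.4%. The figure reproduces and does not depend on the opioid outcomes. The documents give no figure for opioid consumption.

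**Step 3. Inpatient total when discharge patterns differ.** All inputs here are assumed: the same constant opioid rate r in both arms, same-day discharge at h = 6 or 8 hours, and other patients observed to 24 hours. With same-day share p,

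expected inpatient MME = r × [p·h + (1 − p)·24].

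The rate cancels in the ratio between arms. For example, at 60% against 40% with h = 6: 0.6×6 + 0.4×24 = 13.2 and 0.4×6 + 0.6×24 = 16.8, so the ratio is 13.2/16.8 and the difference is 21%.

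| Same-day share, arm A / arm B | Hours, h = 6 | Arm A lower by | Hours, h = 8 | Arm A lower by |
|---|---|---|---|---|
| 50% / 50% | 15.0 / 15.0 | 0% | 16.0 / 16.0 | 0% |
| 55% / 45% | 14.1 / 15.9 | 11% | 15.2 / 16.8 | 10% |
| 60% / 40% | 13.2 / 16.8 | 21% | 14.4 / 17.6 | 18% |
| 70% / 30% | 11.4 / 18.6 | 39% | 12.8 / 19.2 | 33% |

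A simulation used equal need, h = 6, 45 per arm, 2,000 runs and a rank-sum test at 0.05 (a test chosen for illustration, since the plan gives none for this total). It rejected in 4.5%, 7.5%, 12.8% and 39.9% of runs for the four rows. A fixed 0-4 h total, or a 0-24 h total that includes home doses, stayed at about 4 to 6% throughout.

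**Step 4. How far the size depends on the assumed rate.** Compare stays of 24 and 20 hours with equal need. At a constant rate the shorter stay gives (24 − 20)/24 = 17% less. If use instead declines with an assumed 6-hour half-life, the shares of all use that fall within the stay are 1 − 2^(−24/6) = 0.9375 and 1 − 2^(−20/6) = 0.9008. The difference is then (0.9375 − 0.9008)/0.9375 = about 4%. Both are illustrations.

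**Step 5. A shift in timing with identical stays.** Let each arm use T over 24 hours, a share s of it before discharge. The record shows s·T. If the block delays use until after a same-day discharge, s falls and so does the inpatient total, with T unchanged. Section 1.0 reports effects lasting 2 to 24 hours in the cholecystectomy trials it cites, so such a delay is possible; its size is unknown.

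**The case against.** The best defence has four parts.

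- **Uncaptured home use does not by itself separate the arms.** This stands. With equal discharge shares and equal timing of use, the same part is lost in both arms, and the first row of the table shows no difference and 4.5% rejection. Chance imbalance in discharge is ordinary sampling error and does not bias the test.
- **Discharge may be fixed before treatment.** Section 7.0 speaks of planned admission, randomisation is stratified by surgery technique, the linear model for these outcomes includes technique, and the trial is double blind. These make the larger gaps in the table less plausible. They do not exclude an effect on stay, which the plan lists as an outcome, and they do not touch the shift described in Step 5.
- **Section 12 already has a fixed-window opioid comparison.** The Y/N outcome within 4 hours, tested by Fisher's exact test, is not exposed to home use in any important way, since text-message scoring starts only at 8 hours. This stands, but it does not measure an amount. Section 12 also promises caution in interpreting the MME results, which does not supply the missing analysis.
- **The methods paragraph might be read as open-ended**, so that its generic regression covers the inpatient total too. Even so, the total is not named there, and the analysis would be confined to opioid users.

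A reader might infer more than the documents support: that the inpatient total is bound to be biased, that same-day patients count as zero, or that a particular percentage of any reduction is an artefact. Only doses taken at home are missed; doses given in hospital before a same-day discharge are recorded. No stay or opioid rate is stated, so no percentage can be attributed to this trial.

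**Conclusion.** The inconsistency is established from the text alone: the objective names one quantity, the outcome section leaves its window open, and the analysis section treats another quantity in a subset formed after randomisation.

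The weakness of the inpatient total is conditional. It can mislead if treatment changes when patients go home, or moves opioid use from hospital to home; otherwise it is an unbiased comparison of a limited quantity. The range of about 10 to 39% for gaps of 10 to 40 points in same-day discharge rests on the assumed discharge hours, shares and constant rate in Step 3, and a declining rate would shrink it.

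This concerns a secondary outcome and matters for any claim of reduced consumption. It leaves the 4-hour NRS comparison as it is.

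**What to change.** 1. State the same opioid outcomes, with the same windows, in Sections 2, 3 and 12.
2. Analyse 0-4 h MME in all randomised patients, with non-users at 0 MME, alongside the existing Y/N outcome. Name a method suited to many zeros, for example a rank-based test stratified by surgery technique or a two-part model. This needs no new data.
3. If consumption to 24 hours is to be claimed, add a short item to the 8, 12 and 24 h text messages asking for drug, strength and number of doses since discharge; MME cannot be computed from less. Section 7.0 describes texts only for same-day discharge, so send the item also to admitted patients who leave before 24 hours.
4. Report the inpatient total with its scope stated: it ends at discharge and excludes home use.

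The cost is protocol wording and, for item 3, one short entry in an existing REDCap message. The drawback is that home use is self-reported and may be incomplete.
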